8.7 PROTOCOL VIOLATIONS

For Japan only: the Investigator should document any deviation from the protocol regardless of their reasons. Only when the protocol was not followed in order to avoid an immediate hazard to trial subjects or for other medically compelling reason, the principal Investigator should prepare and submit the records explaining the reasons thereof to the sponsor, and retain a copy of the records.

8.8 COMPENSATION AVAILABLE TO THE PATIENT IN THE EVENT OF TRIAL RELATED INJURY

For Japan only: in the event of health injury associated with this trial, the sponsor is responsible for compensation based on the contract signed by the trial site.

10. APPENDICES

10.1 INDUCERS AND STRONG INHIBITORS OF CYP3A4

The information in this table is provided for guidance to investigators and does not preclude the use of these medications if clinically indicated.

Strong Inducers of CYP3A

Carbamazepine
Dexamethasone^a
Phenobarbital/phenobarbitone
Phenytoin
Rifapentine
Rifampin
Rifabutin
St John's wort

Moderate Inducers of CYP3A

Bosentan
Lenisurad
Modafinil
Primidone
Telotristat ethyl

Strong Inhibitors of CYP3A

Aprepitant
Ciprofloxacin
Clarithromycin
Conivaptan
Diltiazem
Erythromycin
Fluconazole
Itraconazole
Ketoconazole
Nefazodone
Posaconazole
Troleandomycin
Verapamil

^a Important note: All patients may receive supportive therapy with dexamethasone, preferably ≤7 days, if clinically indicated.

10.2 PHARMACOKINETICS PLAN

10.2.1 FLOW CHART for PK, immunogenicity, and biomarkers for cohorts A, B, C, and D (dose finding)

10.2.1.1 Flowchart for PK, immunogenicity, and biomarkers for Cohorts A, B, C, and D (dose finding) in treatment course 1

Course	Visit	Day	Planned time [h:min]	Event and comment	Xentuzumab PK	ADA	Total IGF-1/2, IGFBP-3	Free /dissociable IGF-1/2	plIGF-1R/IGF-1R in PRP
SCR	SCR	Within 28d before C1V1	-999:00*	Sampling at screening visit					X
1	1	1	-0:05	Blood sampling prior to xentuzumab infusion	X	X	X	X	X
			0:00	Start of xentuzumab infusion					
			1:00**	Immediately at the end of xentuzumab infusion	X				
	2	8	168:00	Blood sampling ~5 minutes prior to xentuzumab infusion	X	X			X

*Planned time listed at visit SCR is considered to be a dummy planned time to set-up the database, the description in column "Day" defines the timing for these specific samples

** If the infusion duration is different from 1h, please adapt the sampling time accordingly.

Proprietary confidential information © 2024 Boehringer Ingelheim International GmbH or one or more of its affiliated companies

10.2.1.2 FLOW CHART for PK, immunogenicity, and biomarkers for cohorts A, B, C, and D (dose finding) in courses 2-12, 15, and 18, EOTV and FU

Course	Visit	Day	Planned time [h:min]	Event and comment	Xentuzumab PK	ADA	Total IGF-1/2, IGFBP-3	Free /dissociable IGF-1/2	pIGF-1R/IGF-1R in PRP
2-12, 15, 18	1	1	-0:05	Blood sampling prior to xentuzumab infusion	X	X	X	X	X
			0:00	Start of xentuzumab infusion					
			1:00**	Immediately at the end of xentuzumab infusion	X				
EOTV	EOTV	Within 7d after last drug intake	998:00*	End of treatment visit	X	X	X	X	X
FU	FU	42 +7d after last drug intake	999:00*	Follow-up	X	X	X	X	X

*Planned times listed at visit EOTV and FU are considered to be dummy planned times to set-up the database, the description in column "Day" defines the timing for these specific samples

** If the infusion duration is different from 1h, please adapt the sampling time accordingly.

10.2.2 FLOW CHART for PK, immunogenicity, and biomarkers for cohort E

10.2.2.1 FLOW CHART for PK, immunogenicity, and biomarkers for cohort E in Run-in phase and treatment course 1

Course	Visit	Day	Planned time [h:min]	Event and comment	Xentuzumab PK	ADA	Abemaciclib and metabolites PK***	Total IGF-1/2, IGFBP-3	Free/dissociable IGF-1/2	pIGF-IR/IGF-IR in PRP
SCR	SCR	Within 28d before Run in V1	-999:00*	Sampling at screening visit						X
Run in	1	-9	-192:05	5 minutes prior to first abemaciclib treatment	X	X	X***	X	X	X
			-0:05	Blood sampling 5 minutes prior to abemaciclib administration			X***			
			0:00	abemaciclib administration (morning dose)						
			1:00			X				
			2:30			X				
			4:00			X				
			6:00			X				
			8:00			X				
			12:00 [± 2:00]	Blood sampling before intake of evening dose of abemaciclib			X			
1	1	1	-0:05	Blood sampling prior to xentuzumab infusion and abemaciclib administration	X	X	X***	X	X	X
			0:00	Start of xentuzumab infusion						
			0:01	Abemaciclib administration						
			1:00**	Immediately at the end of xentuzumab infusion	X					
	2	8	168:00	Blood sampling prior to xentuzumab infusion	X	X				X

*Planned time listed at visit SCR is considered to be a dummy planned time to set-up the database, the description in column "Day" defines the timing for these specific samples

** If the infusion duration is different from 1h, please adapt the sampling time accordingly.

*** At days of abemaciclib PK sampling, patients have to take their morning dose of abemaciclib in the hospital in order to allow exact timing of PK sampling

10.2.2.2 FLOW CHART for PK, immunogenicity, and biomarkers for cohort E in treatment course 2

Course	Visit	Day	Planned time [h:min]	Event and comment	Xentuzumab PK	ADA	Abemaciclib and metabolites PK***	Total IGF-1/2, IGFBP-3	Free dissociable IGF-1/2	pIGF-1R/IGF-1R in PRP
2	1	1	-0:05	Blood sampling prior to abemaciclib and xentuzumab administration	X	X	X***	X	X	X
			0:00	Start of xentuzumab infusion						
			0:01	Abemaciclib administration						
			1:00**	Immediately at the end of xentuzumab infusion	X		X			
			2:30		X		X			
			4:00		X		X			
			6:00		X		X			
			8:00		X		X			
			12:00 [± 2:00]	Blood sampling before intake of evening dose of abemaciclib	X		X			
	1	2	23:55	Blood sampling prior to abemaciclib administration	X					
			24:00	Abemaciclib administration						
1b	4±1	72:00		Blood sampling at this visit	X					
2	8±1	168:00		Blood sampling ~ 5 min prior to abemaciclib administration and xentuzumab infusion	X					

** If the infusion duration is different from 1h, please adapt the sampling time accordingly.

*** At days of abemaciclib PK sampling, patients have to take their morning dose of abemaciclib in the hospital in order to allow exact timing of PK sampling

10.2.2.3 FLOW CHART for PK, immunogenicity, and biomarkers for cohort E in treatment courses 3-12, 15, 18 and EOTV and FU visit

Course	Visit	Day	Planned Time [h:min]	Event and comment	Xentuzumab PK	ADA	Abemaciclib and metabolites PK	Total IGF-1/2, IGFBP-3	Free /dissociable IGF-1/2	pIGF-1R/IGF-1R in PRP
3-12, 15, 18	1	1	-0:05	Blood sampling prior to abemaciclib administration and xentuzumab infusion	X	X		X	X	X
			0:00	Start of xentuzumab infusion						
			0:01	Abemaciclib administration						
			1:00**	Immediately at the end of xentuzumab infusion	X					
EOTV	EOTV	Within 7d after last drug intake	998:00*	End of treatment visit	X	X		X	X	X
FU	FU	42 +7d after last drug intake	999:00*	Follow-up	X	X		X	X	X

*Planned times listed at visit EOTV and FU are considered to be dummy planned times to set-up the database, the description in column "Day" defines the timing for these specific samples

** If the infusion duration is different from 1h, please adapt the sampling time accordingly.

10.2.3 FLOW CHART for PK, immunogenicity, and biomarkers for cohort F

As of 22 Oct 2021, samples for PK, immunogenicity and biomarkers are no longer collected for ongoing patients.

10.2.3.1 FLOW CHART for PK, immunogenicity, and biomarkers for cohort F in screening and treatment course 1

Course	Visit	Day	Planned time [h:min]	Event and comment	Xentuzumab PK	ADA	Abemaciclib and metabolites PK**	Total IGF-1/2, IGFBP-3	Free /dissociable	pIGF-1R/IGF-1R in PRP
SCR	SCR	Within 28d before Run in V1	-999:00	Sampling at screening visit						X
1	1	1	-0:05	Blood sampling prior to abemaciclib administration, xentuzumab infusion and fulvestrant injection	X	X	X***	X	X	X
			0:00	Start of xentuzumab infusion						
			0:01	Abemaciclib administration						
			0:00	Fulvestrant injection up to 15min. after start of xentuzumab infusion						
			1:00**	Immediately at the end of xentuzumab infusion	X					
	2	8	168:00	Blood sampling prior to xentuzumab infusion	X	X				X

*Planned time listed at visit SCR is considered to be a dummy planned time to set-up the database, the description in column "Day" defines the timing for these specific samples

** If the infusion duration is different from 1h, please adapt the sampling time accordingly.

*** At days of abemaciclib PK sampling, patients have to take their morning dose of abemaciclib in the hospital in order to allow exact timing of PK sampling

10.2.3.2 FLOW CHART for PK, Immunogenicity, biomarkers for cohort F in treatment courses 2-12, 15, 18, EOTV and FU

Course	Visit	Day	Planned time [h:min]	Event and comment	Xentuzumab PK	ADA	Abemaciclib and metabolites PK	Fulvestrant PK	Total IGF-1/2, IGFBP-3	Free /dissociable IGF-1/2	pIGF-1R/IGF-1R in PRP
2-12, 15, 18	1	1	-0:05	Blood sampling prior to abemaciclib administration, xentuzumab infusion and fulvestrant injection	X	X	X ¹ ***	X ¹	X	X	X
			0:00	Start of xentuzumab infusion							
			0:01	Abemaciclib administration							
			0:00	Fulvestrant injection up to 15min. after start of xentuzumab infusion							
			1:00**	Immediately at the end of xentuzumab infusion	X						
EOTV	EOTV	Within 7d after last drug intake	998:00*	End of treatment visit	X	X			X	X	X
FU	FU	42 +7d after last drug intake	999:00*	Follow-up	X	X			X	X	X

*Planned times listed at visit EOTV and FU are considered to be dummy planned times to set-up the database, the description in column "Day" defines the timing for these specific samples

** If the infusion duration is different from 1h, please adapt the sampling time accordingly.

*** At days of abemaciclib PK sampling, patients have to take their morning dose of abemaciclib in the hospital in order to allow exact timing of PK sampling

¹ this sample needs to be collected in course 2 and 3 only

10.2.4 FLOW CHART for PK, immunogenicity, and biomarkers for cohorts D1 and D2

As of 22 Oct 2021, samples for PK, immunogenicity and biomarkers are no longer collected for ongoing patients.

10.2.4.1 FLOW CHART for PK, immunogenicity, and biomarkers for cohorts D1 and D2 in treatment course 1

Course	Visit	Day	Planned time [h:min]	Event and comment	Xentuzumab PK	ADA	Abemaciclib and metabolites PK	Total IGF-1/2, IGFBP-3	Free/dissociable	pIGF-1R/IGF-1R in PRP
SCR	SCR	Within 28d before C1V1	-999:00*	Sampling at screening visit						X
1	1	1	-0:05	Blood sampling prior to abemaciclib administration, xentuzumab infusion and fulvestrant injection	X	X		X	X	X
			0:00	Start of xentuzumab infusion						
			0:01	Abemaciclib administration						
			0:00	Fulvestrant injection up to 15min. after start of xentuzumab infusion						
			1:00**	Immediately at the end of xentuzumab infusion	X					
	2	8	168:00	Blood sampling prior to xentuzumab infusion	X	X				X
	3	15	336:00	Blood sampling prior to xentuzumab infusion	X					
	4	22	504:00	Blood sampling prior to xentuzumab infusion	X					

*Planned time listed at visit SCR is considered to be a dummy planned time to set-up the database, the description in column "Day" defines the timing for these specific samples

** If the infusion duration is different from 1h, please adapt the sampling time accordingly.

10.2.4.2 FLOW CHART for PK, immunogenicity, and biomarkers for cohorts D1 and D2 in treatment course 2

Course	Visit	Day	Planned time [h:min]	Event and comment	Xentuzumab PK	ADA	Abemaciclib and metabolites PK***	Fulvestrant PK	Total IGF-1/2, IGFBP-3	Free / dissociable IGF-1/2	pIGF-1R/IGF-1R in PRP
2	1	1	-0:05	Blood sampling prior to abemaciclib administration, xentuzumab infusion and fulvestrant injection	X	X	X***	X	X	X	X
			0:00	Start of xentuzumab infusion							
			0:01	Abemaciclib administration							
			0:00	Fulvestrant injection up to 15min. after start of xentuzumab infusion							
			1:00**	Immediately at the end of xentuzumab infusion	X		X ¹	X ¹			
			2:30		X ¹		X ¹				
			4:00		X ¹		X ¹				
			6:00		X ¹		X ¹				
			8:00		X ¹		X ¹				
			12:00 [± 2:00]	Blood sampling ~5 minutes before intake of evening dose of abemaciclib	X ¹		X ¹	X ¹			
	1	2	23:55		X ¹			X ¹			
			24:00	Abemaciclib administration							
1b	4	72:00		Blood sampling prior to abemaciclib administration	X ¹			X ¹			
2	8	168:00		Blood sampling prior to xentuzumab infusion	X ¹			X ¹			
3	15	336:00		Blood sampling prior to xentuzumab infusion				X ¹			
4	22	504:00		Blood sampling prior to xentuzumab infusion				X ¹			

** If the infusion duration is different from 1h, please adapt the planned time accordingly.

*** At days of abemaciclib PK sampling, patients have to take their morning dose of abemaciclib in the hospital in order to allow exact timing of PK sampling

¹ these PK samples will be collected for at least 15 subjects in cohort D1 and at least 15 subjects in cohort D2.

10.2.4.3 FLOW CHART for PK, Immunogenicity, biomarkers for cohorts D1 and D2 in treatment courses 3, 4, 6, 12, 24, EOTV and FU

Course	Visit	Day	Planned time [h:min]	Event and comment	Xentuzumab PK	ADA	Abemaciclib and metabolites PK	Fulvestrant PK	Total IGF-1/2, IGFBP-3	Free /dissociable IGF-1/2	pIGF-1R/IGF-1R in PRP
3, 4, 6, 12, 24	1	1	-0:05	Blood sampling prior to abemaciclib administration, xentuzumab infusion and fulvestrant injection	X	X	X ¹	X ¹	X ²	X ²	X
			0:00	Start of xentuzumab infusion							
EOTV	EOTV	Within 7d after last drug intake	998:00*	End of treatment visit	X	X			X	X	X
FU	FU	42 +7d after last drug intake	999:00*	Follow-up	X	X			X	X	X

*Planned times listed at visit EOTV and FU are considered to be dummy planned times to set-up the database, the description in column "Day" defines the timing for these specific samples

¹ this sample needs to be collected in course 3 and course 4 only

² this sample needs to be collected in course 3, course 4, and course 6 only

10.3 TUMOUR TISSUE SAMPLE REQUIREMENTS

Marker category	Tissue type	Amount of tissue	Time point of sample taking	Analysis type
PGx	FFPE (RNase-free)	Preferably FFPE tumour tissue block for preparation of 8x 5µm sections	screening	RNA expression
PGx/Protein Biomarkers	FFPE	Preferably FFPE tumour tissue block for preparation of 17x 5µm sections	screening	DNA isolation + mutational/CNA analysis and biochemical protein analysis (e.g. IHC)

10.4 TUMOUR RESPONSE ASSESSMENT ACCORDING TO RECIST 1.1

Response criteria for target lesions

1. Complete Response (CR):	Disappearance of all target lesions. Any pathological lymph nodes (whether target or non-target) must have a reduction in short axis to <10mm)
2. Partial Response (PR):	At least a 30% decrease in the sum of diameters of target lesions taking as reference the baseline sum diameters
3. Progression (PD):	At least a 20% increase in the sum of diameters of target lesions, taking as references the smallest sum on study (this includes the baseline sum if that is the smallest on study). In addition to the relative increase of 20%, the sum must also demonstrate an absolute increase of at least 5mm (note: the appearance of one or more new lesions is also considered progression).
4. Stable Disease (SD):	Neither sufficient shrinkage to qualify for PR nor sufficient increase to qualify for PD, taking as references the smallest sum diameters while on study

Response criteria for non-target lesions

1. Complete Response (CR):	Disappearance of all non-target lesions and normalization of tumour marker level. All lymph nodes must be non-pathological in size (<10mm short axis)
2. Non-CR/ Non-PD:	Persistence of one or more non-target lesion(s) or/and maintenance of tumour marker level above the normal limits
3. Progression (PD):	Unequivocal progression of existing non-target lesions (Note: the appearance of one or more new lesions is also considered progression)

Time point response for patients with measurable disease at baseline

Target lesions	Non-Target lesions	New lesions	Overall response
CR	CR	No	CR
CR	Non-CR/Non-PD	No	PR
CR	Not evaluated	No	PR
PR	Non-PD or not all evaluated	No	PR
SD	Non-PD or not all evaluated	No	SD
Not all evaluated	Non-PD	No	NE
PD	Any	Yes or No	PD
Any	PD	Yes or No	PD
Any	Any	Yes	PD

Time point response for patients with non-measurable disease at baseline

Non-target lesions	New lesions	Overall response
CR	No	CR
Non-CR/ Non-PD	No	Non-CR/ Non-PD
Not all evaluated	No	NE
Unequivocal PD	Yes or No	PD
Any	Yes	PD

RECIST 1.1 is as published in Eur. J. Cancer [R09-0262](#)

Best overall response is evaluated from first treatment administration until the earliest of disease progression, death or last evaluable tumour assessment before start of subsequent anti-cancer therapy. When stable disease is believed to be best response, it must also meet a minimum time from first treatment administration of 48 days (i.e. according [Flow Chart](#), the first post-baseline imaging should be performed within 63 days after start of xentuzumab). Note that clinical disease assessment will not be considered for determination of best overall response. No confirmation is required for best overall response

10.5 CLINICAL EVALUATION OF LIVER INJURY

10.5.1 Introduction

Alterations of liver parameters, as described in [Section 5.3.6.1](#) (Protocol-Specified Adverse events of special interest), are to be further evaluated using the following procedures:

10.5.2 Procedures

Any elevation of ALT/AST and bilirubin qualifying as laboratory alert should be confirmed using the initial sample if possible.

If the alert is confirmed on initial sample, or it is not possible to repeat testing using initial sample, the following must be completed:

- 1) Evaluate patient within 48 hours and
- 2) Perform the following laboratory tests:
 1. Repeat of AST, ALT, bilirubin (with fractionation to total and direct)
 2. Haptoglobin
 3. Complete blood count and cell morphology
 4. Reticulocyte count
 5. Creatine Kinase (CK)
 6. Lactate dehydrogenase (LDH)
 7. Alkaline Phosphatase

The results of these laboratory tests must be reported to BI as soon as possible.

If the initial alert values (i.e. AST, ALT, and bilirubin) are confirmed on the second sample described as above, then an abdominal ultrasound or clinically appropriate alternate imaging (to rule out biliary tract, pancreatic or intrahepatic pathology, e.g. bile duct stones or neoplasm) must be completed within 48 hours.

The findings from the hepatic imaging (including comparison to prior imaging if available) must be made available as soon as possible as part of the adverse event reporting process. In the event the etiology of the abnormal liver tests results is not identified based on the imaging (e.g. biliary tract, pancreatic or intrahepatic pathology), then the “DILI checklist” must be completed. Details of the “DILI checklist” are provided in the ISF. The following assessments need to be performed in order to complete the “DILI checklist” and results will be reported via the eCRF:

obtain a detailed history of current symptoms and concurrent diagnoses and medical history according to the “DILI checklist” provided in the ISF;

obtain history of concomitant drug use (including non-prescription medications, herbal and dietary supplement preparations), alcohol use, recreational drug use, and special diets according to the “DILI checklist” provided in the ISF;

obtain a history of exposure to environmental chemical agents (consider home and work place exposure) according to the “DILI checklist” provided in the ISF;

complete the following laboratory tests as detailed in the DILI checklist provided in the ISF:
Clinical chemistry

Alkaline phosphatase, cholinesterase (serum)*, albumin, PT or INR, CK, CK-MB, coaguloplasmin*, α -1 antitrypsin*, transferrin*, amylase, lipase, fasting glucose, cholesterol, triglycerides

Serology

Hepatitis A (Anti-IgM, Anti-IgG), Hepatitis B (HbsAg, Anti-HBs, DNA), Hepatitis C (Anti-HCV, RNA if Anti-HCV positive), Hepatitis D (Anti-IgM, Anti-IgG), Hepatitis E (Anti-HEV, Anti-HEV IgM, RNA if Anti-HEV IgM positive), Anti-Smooth Muscle antibody (titer), Anti-nuclear antibody (titer), Anti-LKM (liver-kidney microsomes) antibody, Anti-mitochondrial antibody, Epstein Barr Virus (VCA IgG, VCA IgM), cytomegalovirus (IgG, IgM), herpes simplex virus (IgG, IgM)*, varicella (IgG, IgM)*, parvovirus (IgG, IgM)*

Hormones, tumour marker

Thyroid-stimulating hormone (TSH)*

Haematology

Thrombocytes, eosinophils

*If clinically indicated (e.g. immunocompromised patients)

Long term follow-up

Initiate close observation of subjects by repeat testing of ALT, AST, and bilirubin (with fractionation to total and direct) at least weekly until the laboratory ALT and or AST abnormalities stabilize or return to normal, then according to the protocol. Depending on further laboratory changes, additional parameters identified e.g. by reflex testing will be followed up based on medical judgement and Good Clinical Practices (GCP). and report these via the eCRF.

10.6 STATISTICAL APPENDIX

A Bayesian logistic regression model with overdose control will be used to guide dose escalation/ de-escalation in cohorts A, B, C and D(dose finding). The BLRM is introduced in [Section 7.1](#), which also specifies the prior for the model in cohort A. The priors for other dose finding cohorts (B, C and D(dose finding)) will be documented in the TSAP. After patients in each dose group have completed at least one course of treatment, the prior distributions will be updated through Gibbs sampling procedures with the accumulated DLT data from the MTD evaluation period. Posterior probabilities for the rate of DLT will be summarised from BLRM. Selection of the next dose combinations will be based on these probabilities as well as on other safety and laboratory data.

The purpose of this statistical appendix is to present performance metrics (operating characteristics) that illustrate the precision of the design in estimating the MTD under various dose-toxicity relationships through computer simulation. These results are summarized in [Table 10.6: 3](#). In addition, recommendations of the next dose combination by the BLRM with overdose control principle are also provided under various hypothetical outcome scenarios in

early dose groups to show how it facilitates on-study dose-escalation decisions (see [Table 10.6: 1](#)).

Hypothetical data scenarios

Hypothetical data scenarios are shown in [Table 10.6: 1](#). These scenarios reflect potential on-study data constellations and related escalation as allowed by the model. For each scenario, the probability of target dose and overdose for the current dose combination, as well as the next potential dose combination and related probabilities of under-dosing, target dose, and over-dosing are shown.

For example, scenario 1 shows the example, that at the starting dose combination 150 mg abemaciclib and 1000 mg xentuzumab none of 3 patients experiences a DLT. Then, the BLRM allows treating patients at the same dose which is the maximum combination dose allows by the protocol.

Scenario 4 shows the example, that at the starting dose combination 150 mg abemaciclib and 1000 mg xentuzumab none of 6 patients experiences a DLT. Therefore, the MTD in this case would be the combination of 150 mg / 1000 mg.

Scenario 6 shows the example that at the starting dose combination 150 mg abemaciclib and 1000 mg xentuzumab 2 out of 3 patients experiences a DLT, then none of 3 patients treated at 100 mg / 1000 mg experiences a DLT. The overdose control of the BLRM suggests escalating to 150 mg / 750 mg.

All these scenarios illustrate the adaptive behaviour of the model even in extreme situations.

Table 10.6: 1 Hypothetical data scenarios for cohort A

Scenario	Dose combination (mg/mg)	# patient / # DLT	Current dose combination		Next recommended dose combination*	Next dose combination		
			P(TD)	P(OD)		P(UD)	P(TD)	P(OD)
1	150/1000	3 / 0	0.179	0.027	150/1000	0.794	0.179	0.027
2	150/1000	3 / 1	0.376	0.141	150/1000	0.483	0.376	0.141
3	150/1000	3 / 2	0.397	0.430	100/1000	0.473	0.365	0.162
4	150/1000 150/1000	3 / 0 3 / 0	0.116	0.009	150/1000	0.876	0.116	0.009
5	150/1000 150/1000	3 / 1 3 / 0	0.312	0.048	150/1000	0.640	0.312	0.048
6	150/1000 100/1000	3 / 2 3 / 0	0.309	0.053	150/750	0.324	0.491	0.185

Table 10.6: 1 (cont.) Hypothetical data scenarios for cohort A

Scenario	Dose combination (mg/mg)	# patient / # DLT	Current dose combination		Next recommended dose combination*	Next dose combination		
7	150/1000	3 / 2	0.428	0.081	100/1000	0.491	0.428	0.081
	100/1000	3 / 0						
	100/1000	3 / 1						

* Recommended dose combination is the dose combination with the highest target probability. Note that other combinations have similar target toxicity probabilities.

Operating characteristics

Operating characteristics are a way to assess the long-run behaviour of a model by illustrating the precision of the design in estimating the MTD. Under an assumed true dose-toxicity curve, metrics such as the probability of recommending a dose combination with true DLT rate in the target interval can be approximated via simulation.

[Table 10.6: 2](#) describes 4 assumed true dose-toxicity scenarios which were used to assess the operating characteristics of this model. These scenarios reflect a wide range of possible cases as follows:

- * Scenario 1: aligned with prior means
- * Scenario 2: high-toxicity scenario
- * Scenario 3: low-toxicity scenario
- * Scenario 4: low-high-toxicity scenario

Table 10.6: 2 Assumed true dose-toxicity scenarios for cohort A

Dose combination (mg/mg)	P(DLT)	Scenario			
		1: Prior	2: High Tox	3: Low Tox	4: Low-High
100/750	P(DLT)	0.083	0.16	0.03	0.08
150/750		0.137	0.24	0.08	0.16
100/1000		0.092	0.17	0.06	0.10
150/1000		0.150	0.31	0.10	0.20

For each of these scenarios, 1000 trials were simulated. Each cohort consisted of 3 patients and dose escalation complied with the following rule:

- Escalate to the dose combination which maximises the probability of the targeted toxicity region and satisfies the overdose criterion

The MTD was considered reached if at least 6 patients have been evaluated at a dose combination which is the model's recommendation for the next dose-level cohort and for which the posterior probability of targeted toxicity was at least 50%. Or if in total 6 patients have been evaluated at a dose combination which is the model's recommendation for the next dose-level cohort.

It was then assessed how often a dose combination was declared as MTD with true DLT rate in the under-, targeted or over-dose range.

Furthermore, the average, minimum and maximum number of patients per trial and the average number of DLTs per trial are reported. Results are shown in [Table 10.6: 3](#) below.

Table 10.6: 3 Simulated operating characteristics for cohort A

Scenario	% of trials declaring a MTD with true DLT rate in				# Patients	# DLTs
	underdose	target dose	overdose	Stopped	Mean (Min-Max)	Mean (Min-Max)
1: Prior	43.7	54.3	0	2.0	10.86 (3, 21)	2.19 (0, 8)
2: High Tox	0	68.3	23.3	8.4	10.68 (3, 21)	3.10 (1, 9)
3: Low Tox	23.9	73.3	0	2.8	11.94 (3, 21)	1.75 (0, 7)
4: Low-High	3.9	55.1	38.9	2.1	12.10 (3, 21)	2.91 (1, 9)

In scenario 1, which reflects the case that the true dose-toxicity is aligned with prior means, almost all of the simulated trials (54%) that have found a MTD declared the MTD with true toxicity rate in the target interval. Few simulated trials (2.0%) have been stopped before declaring a MTD. None of trials declared a MTD with true DLT rate in the overdose interval.

In scenario 2 (high-toxicity scenario) 68% of the simulated trials that have found a MTD declared the MTD with true toxicity rate in the target interval and 23% declared a MTD with true DLT rate in the overdose interval. Few simulated trials (8%) have been stopped before declaring a MTD.

Scenario 3 (low-toxicity scenario) illustrates a behaviour similar to scenario 1.

Scenario 4, a mixture of the high toxicity and the low toxicity scenario, shows characteristics of both of these.

The mean patient numbers range from 10.68 patients (Scenario 2) to 12.10 patients (Scenario 4) and the maximum number of patients was 21. Therefore, the patient numbers are as expected.

By reviewing the metrics presented, it can be seen that the model is not sensitive to different scenarios of truth. In general, this model is conservative due to the overdose control criteria. In all scenarios, the probabilities of recommending a dose combination with true $P(DLT) \geq 33\%$ as MTD are much smaller than probabilities of recommending a dose combination with true $P(DLT)$ between 16% and 33% as MTD.

On-study recommendations based on the model are consistent with the clinical decision making process, and should be considered in conjunction with other available clinical information by the SC in deciding the dose levels to be tested in order to determine the MTD estimates.

R version 3.2.2 was used for data scenarios and simulations.

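### Tables 10.6:2 and 10.6:3 contradict each other: four target/overdose percentages and three mean DLT counts are impossible under the listed true DLT rates, and the surrounding text fails whichever table is right

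*Protocol*

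**What the plan says.** Protocol Section 7.1 divides the DLT probability into underdosing (below 0.16), target (0.16 to below 0.33) and overdosing (0.33 and above). Appendix 10.6 then presents simulations intended to "illustrate the precision of the design in estimating the MTD under various dose-toxicity relationships through computer simulation".

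Table 10.6:2, "Assumed true dose-toxicity scenarios for cohort A", gives a true DLT rate for each of four combinations in four scenarios. Table 10.6:3 gives, from 1000 simulated trials per scenario, the percentage declaring an MTD in each category, the percentage stopped, and the mean numbers of patients and DLTs.

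The text says that in Scenario 1 "almost all of the simulated trials (54%) that have found a MTD declared the MTD with true toxicity rate in the target interval", and that in Scenario 2 "23% declared a MTD with true DLT rate in the overdose interval". It concludes that "the model is not sensitive to different scenarios of truth" and that "In general, this model is conservative due to the overdose control criteria". It adds that in all scenarios the probabilities of recommending an overdose combination "are much smaller than probabilities of recommending a dose combination with true" DLT probability in the target range.

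Two clauses define when the simulated MTD is reached. The first needs at least six patients at the recommended combination and a posterior target probability of at least 50%. The second begins "Or if in total 6 patients have been evaluated at a dose combination" and asks only that this combination be the model's next recommendation.

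Section 7.7 cites the simulation for a mean of about 12 patients in cohort A and assumes the same number for cohorts B, C and D.

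**The concern.** A simulated trial can only declare one of the listed combinations as the MTD. If no listed combination has a true rate in the target or overdose range, the percentage for that category must be zero. Table 10.6:3 prints substantial percentages in such categories. The mean DLT counts also look too high for the listed rates and patient numbers.

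Table 10.6:3 is the protocol's evidence on how well the design finds the MTD, which is a primary endpoint of cohorts A to D. The dose-finding cohort size also leans on it: about 48 of roughly 148 patients. If the table does not describe the stated scenarios, the reader has no valid operating characteristics.

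**Working it through.** **Inputs.** Intervals from Section 7.1; true rates from Table 10.6:2; results from Table 10.6:3.

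**1. Is the printed text intact?** The rows of Table 10.6:3 sum to 100:
- S1: 43.7 + 54.3 + 0 + 2.0
- S2: 0 + 68.3 + 23.3 + 8.4
- S3: 23.9 + 73.3 + 0 + 2.8
- S4: 3.9 + 55.1 + 38.9 + 2.1

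The prose repeats the Scenario 1 and 2 figures, and the Scenario 1 rates in Table 10.6:2 equal the prior means in Table 7.1:4. An extraction fault is unlikely.

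**2. Classify the true rates** (U = under, T = target, O = over; combinations are abemaciclib/xentuzumab in mg).

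| Scenario | 100/750 | 150/750 | 100/1000 | 150/1000 | Printed, but must be 0% |
|---|---|---|---|---|---|
| 1 | 0.083 U | 0.137 U | 0.092 U | 0.150 U | target 54.3 |
| 2 | 0.16 T | 0.24 T | 0.17 T | 0.31 T | overdose 23.3 |
| 3 | 0.03 U | 0.08 U | 0.06 U | 0.10 U | target 73.3 |
| 4 | 0.08 U | 0.16 T | 0.10 U | 0.20 T | overdose 38.9 |

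No combination in any scenario is an overdose. This does not depend on the starting combination or the stopping rule.

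**3. Bound the mean DLT count.** Each patient's DLT probability is at most the highest listed rate p. So, for any stopping rule based on past data, mean DLTs ≤ p × mean N. The Monte Carlo standard error is taken as √(p(1−p) × mean N / 1000).

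| Scenario | p × mean N | Printed mean DLTs | Excess | SE | Excess/SE | Mean N needed at rate p |
|---|---|---|---|---|---|---|
| 1 | 0.150 × 10.86 = 1.629 | 2.19 | 0.561 | 0.0372 | 15.1 | 2.19/0.150 = 14.6 |
| 2 | 0.31 × 10.68 = 3.311 | 3.10 | none | – | – | – |
| 3 | 0.10 × 11.94 = 1.194 | 1.75 | 0.556 | 0.0328 | 17.0 | 1.75/0.10 = 17.5 |
| 4 | 0.20 × 12.10 = 2.420 | 2.91 | 0.490 | 0.0440 | 11.1 | 2.91/0.20 = 14.55 |

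Scenario 2 is compatible; Scenarios 1, 3 and 4 are not. The result does not use the category cut-offs.

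**4. Test the text under each table.**
- *If Table 10.6:3 is right:* 54.3% (54.3/98.0 = 55.4% of trials that declared an MTD) is not nearly all. The 68% for Scenario 2 is worded as a share of trials that found an MTD, which would be 68.3/91.6 = 74.6%. Scenario 4 overdose is 38.9/55.1 = 0.71 of target, which is not much smaller. Overdose running from 0% to 38.9% across scenarios does not fit a claim of insensitivity.
- *If Table 10.6:2 is right:* the quoted 54% and 23% should both be 0%. No scenario contains a true overdose, so the overdose claim was not tested.

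**5. Stopping rule.** A trial with six patients at the recommended combination already meets the second clause, so the first clause's 50% condition never matters. The description of the simulation also does not state its starting combination.

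**6. Supporting check.** The model was rebuilt from the Table 7.1:3 priors. It assumed a 150/1000 start, cohorts of three, a 25% overdose limit and a 21-patient cap taken from the printed maximum. It matched the Table 7.1:4 means and Table 10.6:1 to within about 0.01. It did not reproduce Table 10.6:3: mean N was 6.2 to 7.6 under the six-patient rule, and 14.9 to 20.0 when a target probability of at least 0.50 was also required, against 10.68 to 12.10 printed. Steps 2 to 4 do not rely on this.

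**The case against.** The strongest reply is that Table 10.6:2 may be incomplete rather than wrong. A more toxic combination that was simulated but not listed could produce both the impossible cells and the high DLT counts. That is possible, but Table 10.6:2 would then misdescribe the scenarios used. It would also conflict with Section 4.1.2.1, which rules out going above the planned levels, and with Appendix 10.6, which treats 150/1000 as the maximum.

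Unstated cut-offs (lower about 0.084 to 0.10, upper about 0.161 to 0.20) would make the four cells possible. They contradict Section 7.1 and the 16% and 33% limits repeated in Appendix 10.6, and they leave the mean DLT problem untouched.

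Some points on the other side stand:
- Not every sentence fails. The absence of overdoses in Scenario 1 is true under both tables, and the stopped percentages and patient numbers match Table 10.6:3.
- The missing starting combination is minor, because Sections 4.1.2.1 and 7.1 and Table 10.6:1 all start at 150/1000.
- Practical impact is limited. Section 7.7 disclaims a formal power calculation and allows more or fewer patients. Dose decisions rest on observed DLTs, overdose control and the Steering Committee. Section 4.1.2.1 requires six evaluable patients at the selected dose before Part 2. SAP Section 3 reports that the safety analyses after the dose-finding cohorts were performed.

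**Conclusion.** The concern holds. Given the Section 7.1 intervals, four cells printed as 54.3, 73.3, 23.3 and 38.9 must be 0%. Three mean DLT counts exceed their maxima by 0.56, 0.56 and 0.49 per trial, or 11 to 17 Monte Carlo standard errors. Both results need only the printed numbers and the assumption that Table 10.6:2 lists every combination simulated.

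The documents do not establish which table is wrong. The match between Scenario 1 and Table 7.1:4 makes Table 10.6:3 the more suspect, at least for that scenario.

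The mean of about 12 patients in Section 7.7 is unsupported as written, not refuted. The overdose-control rule, Table 7.1:4 and Table 10.6:1 are not in question, and no recommended dose is shown to be wrong. This is a should-fix correction of stated operating characteristics, not of trial conduct.

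**What to change.** Identify the true rates, starting combination and stopping rule that were actually simulated. Then correct or re-run the simulation so that Tables 10.6:2 and 10.6:3 and the text after them agree. State the starting combination and a single stopping rule with no redundant clause.

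Keep the statements on near-universal correct selection, conservatism, insensitivity and low overdose probability only where the corrected results support them. If the overdose statement stays, include at least one scenario with a combination whose true rate is 0.33 or more. Restate the cohort A mean in Section 7.7, and the assumption carried to cohorts B to D, from the corrected output.

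The cost is tracing or repeating a simulation and replacing tables and text. No patients, procedures or endpoint analyses change, and no dose or clinical rule is proposed. Some stated properties may look less favourable.
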